8.7.1.4 Comparative analyses

Relative risks (HRs) for the defined outcomes will be estimated using Cox models with time-varying covariates if model pre-requisites are fulfilled. HRs will be presented along with 95% CIs.

The Cox models will include the exposure and the comparator group within the model. This will account for multiple testing and for retaining same variables in variable selection (see [Section 8.7.1.6](#)). The models are defined in terms of covariates adjusted for in addition to the primary exposure: (i) baseline model with covariates adjusted for with values at index date (ii) model with time-dependent covariates wherein change in covariates over the follow-up period after index date are also incorporated into the model.

Country-specific analysis:

The country-specific Cox models will be fit with single-country level datasets. The analyses will use datasets from the UK, Sweden, and Finland, separately.

Meta-analysis:

Country-level effect sizes will be pooled using meta-analysis models to compute pooled effect size estimates. Prior to conducting meta-analyses, heterogeneity across the countries in terms of study design and conduct will be assessed. Specifically, the variability in population characteristics (including data availability), propensity score matching variables as well as propensity score balance will be examined.

Meta-analyses will be carried out for analyses where the country-level effect size is available for all three study countries. Pooled effect sizes will be estimated using random-effects models. The inverse-variance method will be used where appropriate.

Statistical heterogeneity between country-level estimates will be assessed using:

- Cochran's Q test
- I^2 statistic and its 95% CI
- The τ^2 statistic and its 95% CI

For each meta-analysis model, results will be presented in a forest plot including at least the following data:

- Data source.
- Effect size and 95% CI for each study included in the analysis (on a log scale).
- The weights allocated to each study.
- The combined estimated effect size with 95% CI (on a log scale) for the random-effects model.
- Value of Cochran's Q statistic, with the number of degrees of freedom and p-value.
- The proportion of variability explained by heterogeneity (I^2).
- The between-study variance τ^2 .

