If high levels of heterogeneity exist, the population characteristics and statistical models in the different country-level analyses will be reviewed and the possible source of heterogeneity discussed. A sensitivity analysis for the main analysis of the primary outcomes will be carried out using fixed-effect models to ascertain the effect of between-study heterogeneity on the meta-analysis result.

Further details regarding the meta-analysis models and heterogeneity will be defined in the study SEAP.

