The τ^2 statistic represents the variance of the distribution of the true effect-sizes. τ^2 will be calculated using the DerSimonian and Laird estimate:

$$\hat{\tau}^2 = \max \left\{ 0, \frac{Q-(K-1)}{\sum_{k=1}^K w_k - \frac{\sum_{k=1}^K w_k^2}{\sum_{k=1}^K w_k}} \right\}; w_k = \frac{1}{s_k^2}$$

where w_k denotes the corresponding weight from the per-country study k , and s_k^2 is the variance of HR estimate of per-country study k .

τ^2 is insensitive to the number of studies or to their precision but can be difficult to interpret. It is however expressed at the same scale as square of the effect size; hence its 95% CI represents the estimated range of true effect sizes.

Random-effects model

The random-effects model considers the observed per-country effect sizes as randomly sampled from a distribution of true effect sizes. The pooled effect size estimated by the model represents the mean of this distribution of true effect sizes.

In addition to the sampling error (squared as variance s_k^2), the random-effects model takes into account the variance of the distribution of the true effects, which is estimated as between-study heterogeneity tau-squared τ^2 . The weight w_k for each country k is calculated with τ^2 as an additional scaling factor, resulting in the adjusted random-effects weights w_k^* .

$$w_k^* = \frac{1}{s_k^2 + \tau^2}$$

The pooled HR estimate $\hat{\theta}$ is calculated using adjusted weights w_k^* .

[figure not shown]
$$\hat{\theta} = \frac{\sum_{k=1}^K \hat{\theta}_k w_k^*}{\sum_{k=1}^K w_k^*}$$

For each meta-analysis, pooled and country-level results will be presented in forest plots similar to Figure 8 showing the following items:

[figure not shown]
- Country identifier
- Number of events (IR/1000 person years) per study group
- HR and 95% CI for each country (on log scale)
- The weight (%) assigned to each country
- The estimated pooled HR and its 95% CI using a random-effect models (on log scale)

Proprietary confidential information © 2024 Boehringer Ingelheim International GmbH or one or more of its affiliated companies

[figure not shown]
- Total number of patients per study group
- Average follow-up time in person years
- Between-study heterogeneity τ^2 and its 95% CI
- The I^2 statistics and its 95% CI

[figure not shown]
Proprietary confidential information © 2024 Boehringer Ingelheim International GmbH or one or more of its affiliated companies

[figure not shown]

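### The SAP misreads the 95% CI of tau-squared as the range of true effects; it is only uncertainty about a variance

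*SAP*

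**What the plan says.** SAP 6.7.3.2 begins correctly: tau-squared "represents the variance of the distribution of the true effect-sizes" and "will be calculated using the DerSimonian and Laird estimate", truncated at zero. The random-effects paragraph that follows is also right: the pooled estimate is the mean of the distribution of true effects.

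Between the two stands the faulty step. The SAP first remarks on the units of tau-squared: "It is however expressed at the same scale as square of the effect size". From that remark about units it then draws this conclusion: "hence its 95% CI represents the estimated range of true effect sizes".

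Tau-squared with its 95% CI is a listed item for each forest plot, and the Figure 8 template has a slot for it. Summing the figure counts in SAP Table 16 gives 87 Figure 8 plots: 18 primary, 54 stratified, 9 secondary and 6 sensitivity. Protocol 8.7.1.4 restricts pooling to analyses "where the country-level effect size is available for all three study countries", so K = 3. It leaves detail to the SAP: "Further details regarding the meta-analysis models and heterogeneity will be defined in the study SEAP". The SAP names no method for the CI of tau-squared and plans no prediction interval.

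**The concern.** The inference does not follow from its premise. If tau-squared is on the scale of the squared effect, its CI is a set of plausible values for a variance. A range for the true log HRs has to be centred on the pooled log HR, with a width that depends on tau and on how well the mean is known. The CI of tau-squared has neither property.

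What is at stake is interpretation. The study asks whether a cancer risk is present and whether the UK, Sweden and Finland agree about it. The sentence is the only instruction on how to read this interval, and a report that followed it would describe agreement with a range wrong in meaning, scale and location.

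**Working it through.** **Inputs** (Protocol 8.5, footnotes to Tables 7 and 8; UK / Sweden / Finland)
- Empagliflozin initiators: 16,360 / 32,334 / 18,269
- Urinary tract cancer rate per 100,000 person-years: 111.5 / 164.5 / 161.5
- Mean follow-up 2.4 / 2.2 / 2.4 years, less the 0.5-year lag: 1.9 / 1.7 / 1.9 years
- Matching: 1:3 / 1:1 / 1:2

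**Assumptions not in the documents**
- Country HRs of 0.65, 0.75 and 0.85, chosen for illustration.
- A Q-profile CI for tau-squared.

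**Reproducing the plan's own figure.** Events per arm = n × (1 − exp(−rate × HR × time)); variance of log HR = 1/e1 + 1/e0. With a DerSimonian-Laird model, K = 3, an SD of 0.1 for the true log HR and two-sided 5%, 40,000 simulated runs at HR 1.5 give power of 93.6% for urinary tract cancer (Table 8: 93.6%) and 83.6% for bladder cancer (84.0%). The precision used below is therefore the plan's own. One mismatch: UK single-country power for urinary tract cancer comes out at 67.1% against 63.7% in Table 7, and matches within 2 points only if follow-up is 2.2 years. This does not affect the argument.

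**Standard errors at HR 1**
- UK: events 34.6 and 103.9; variance 0.0385; SE 0.196
- Sweden: 90.3 and 90.3; 0.0221; SE 0.149
- Finland: 56.0 and 111.9; 0.0268; SE 0.164

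**Pooling the example**
- Log HRs −0.431, −0.288, −0.163; weights 25.97, 45.15, 37.32 (sum 108.43).
- Pooled log HR −0.279, so HR 0.76. SE = 1/√108.43 = 0.096; 95% CI 0.63 to 0.91.
- Q = 0.599 + 0.004 + 0.505 = 1.11. This is below K − 1 = 2, so tau-squared = 0.

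**CI of tau-squared (Q-profile)**
- Lower limit 0, because Q is below the 97.5% chi-square point on 2 df (7.38).
- The upper limit solves Σ(θk − θ̂)²/(sk² + τ²) = 0.0506, the 2.5% point. At τ² = 0.679 the terms are 0.0265 + 0.0000 + 0.0241 = 0.0506. The interval is 0 to 0.68.

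**Reading it as the SAP says.** As log HRs, 0 to 0.68 becomes exp(0) to exp(0.68) = 1.00 to 1.97. All three country HRs and the pooled HR lie outside. On this reading the range could never fall below HR 1, whatever the data.

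**How often this arises.** With no true heterogeneity, tau-squared is estimated as exactly 0 with probability P(chi-square on 2 df < 2) = 63.2%. Given a zero estimate, the median upper limit is 0.39 for urinary tract, 0.66 for bladder and 1.22 for renal cancer. Jackson's method, evaluated at the median Q, gives 0.40, 0.66 and 1.20, so the choice of method matters little. In about 4% of zero-estimate cases the upper limit is also 0.

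**What a correct range looks like.** A 95% prediction interval is θ̂ ± t × √(τ² + SE²). At tau-squared = 0 with t on K − 2 = 1 df (12.71), the factor is exp(12.71 × 0.096) = 3.39. In the example that is 0.22 to 2.56. With a normal quantile the factor would be 1.21, so the quantile has to be stated.

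**The case against.** The strongest reply is that the sentence is explanatory and nothing computed depends on it. This stands. Weights, pooled HRs and their CIs do not use the CI of tau-squared. The interpretive bands in SAP 6.7.3.2 are for I-squared. The Figure 8 template prints tau-squared on its heterogeneity line, and Protocol 8.7.1.4 correctly calls it the between-study variance. The SAP also never tells anyone to exponentiate the interval; reading it as log HRs is one way of taking the sentence literally.

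Four stronger readings are tempting, and the documents do not support them.
- A reader might infer that the misreading decides whether countries are pooled, since SAP 6.7.3 makes pooling conditional on no relevant heterogeneity. That condition does not mention tau-squared or its CI.
- A reader might infer that the interval is too wide when the estimate is zero. The width is genuine: three countries say little about a variance, and a t-based prediction interval is about as wide. The faults are meaning, scale and centring.
- A reader might take the remark that tau-squared "is insensitive to the number of studies or to their precision but can be difficult to interpret" as a second error. It contrasts what tau-squared measures with I-squared, which the SAP says rises with precision. It makes no claim about the width of the CI.
- A reader might place the error in the protocol too. Its forest-plot item "The combined estimated effect size with 95% CI (on a log scale) for the random-effects model" concerns the pooled effect and is sound.

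**Conclusion.** The sentence is wrong as written and should be corrected. It is a minor point: it affects how a printed interval is explained, and no estimate changes. The example (tau-squared CI 0 to 0.68, read as HR 1.00 to 1.97 around a pooled HR of 0.76) rests on invented country HRs, planned precision at HR 1 and an assumed CI method. That the interval has the wrong scale and centre rests on none of these.

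A zero estimate must not be taken to show that the countries agree. In the simulations for urinary tract cancer at HR 1.5, with the protocol's SD of 0.1 applied between countries, tau-squared is still estimated as 0 in about 50% of analyses.

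**What to change.** In SAP 6.7.3.2:
1. Delete the sentence.
2. Describe the 95% CI of tau-squared as uncertainty about the between-country variance.
3. Name the method for that CI.
4. State that three countries estimate heterogeneity poorly, so a zero estimate is not evidence of agreement.

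If a range of true effects is wanted, add a prediction interval centred on the pooled log HR that includes both tau-squared and the standard error of the pooled estimate. State its quantile, and accept that it will be wide with K = 3. Do not use exp(pooled log HR ± 1.96 × tau): it ignores uncertainty in the mean and in tau, and shrinks to a single point whenever tau-squared is estimated as 0.

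The cost is a few lines of SAP text and, if the prediction interval is adopted, one more line on the forest plots. No new data or models are needed.

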6.10. LIST OF PLANNED ANALYSIS

Table 16 List of planned analyses.

Analysis	Details	Exposure definition	Outcomes	Template
Population identification				
Summary of the process used to identify the study populations and study treatment groups.	Country specific analysis (3 figures, one for each country)	N/A	N/A	Figure 2
Population description before matching				
Description of patient baseline characteristics for the study population and the study treatment groups before matching.	Country specific analysis (3 tables, one for each country)	N/A	N/A	Table 17
Assessment of covariate balance before matching				
Balance assessment for baseline characteristics between empagliflozin users at index and DPP-4 inhibitors users at index before matching.	Country specific analysis (3 tables, one for each country)	N/A	N/A	Table 18
Checking overlap in propensity score distribution				
Propensity score distribution plot for empagliflozin users at index and DPP-4 inhibitors users at index.	Country specific analysis (3 figures, one for each country)	N/A	N/A	Figure 3
Assessing the quality of the matching				
Balance assessment for baseline characteristics between empagliflozin users at index and DPP-4 inhibitors users at index after matching.	Country specific analysis (3 tables, one for each country)	N/A	N/A	Table 18
Standardized differences plot before and after PS matching for empagliflozin users at index vs. DPP-4 inhibitors users at index	Country specific analysis (3 figures, one for each country)	N/A	N/A	Figure 4

Analysis	Details	Exposure definition	Outcomes	Template
Propensity score distribution in non-matched empagliflozin users at index date	Country specific analysis			
matched empagliflozin users at index and matched DPP-4 inhibitors users at index.	(3 figures, one for each country)	N/A	N/A	Figure 5
Primary objectives: Descriptive analysis				
Propensity score assessment distribution	Country specific analysis (3 tables, one for each country)	N/A	N/A	Table 19
Stratified incidence rates				
Stratified incidence rates	Using matched cohorts Country specific analysis (9 tables, 3 outcomes x 3 countries)	As treated exposure definition	Main outcomes- Table 8	Table 22
Meta-analysis of incidence rates				
Meta-analysis of incidence rates	Using pooled number of outcome events and person-time from all study countries (3 tables, 3 outcomes)	As treated exposure definition	Main outcomes- Table 8	Table 22
Kaplan-Meier survival probability plots				
Kaplan-Meier survival probability plots	Using matched cohorts Country specific analysis (9 figures, 3 outcomes x 3 countries)	As treated exposure definition	Main outcomes- Table 8	Figure 6
Primary objectives: Comparative analysis				
Hazard ratio estimates using crude model	Using matched cohorts Country specific analysis (18 tables, 2 cohorts x 3 outcomes x 3 countries)	As treated exposure definition	Main outcomes- Table 8	Table 23

Analysis	Details	Exposure definition	Outcomes	Template
Meta-analysis of crude HR estimates	Using adjusted HR estimates and 95% CIs from all study countries (2 cohorts: 6 figures, 3 outcomes)	As treated exposure definition	Main outcomes- Table 8	Figure 8
Hazard ratio estimates using the base model	Using matched cohorts Country specific analysis (18 tables, 2 cohorts x 3 outcomes x 3 countries)	As treated exposure definition	Main outcomes- Table 8	Table 23
Meta-analysis of HR estimates using the base model	Using adjusted HR estimates and 95% CIs from all study countries (2 cohorts: 6 figures, 3 outcomes)	As treated exposure definition	Main outcomes- Table 8	Figure 8
Hazard ratio estimates using the adjusted model	Using matched cohorts Country specific analysis (18 tables, 2 cohorts x 3 outcomes x 3 countries)	As treated exposure definition	Main outcomes- Table 8	Table 25
Meta-analysis of adjusted HR estimates	Using adjusted HR estimates and 95% CIs from all study countries (2 cohorts: 6 figures, 3 outcomes)	As treated exposure definition	Main outcomes- Table 8	Figure 8
Stratified analysis				
Hazard ratio estimates using adjusted model	Using matched cohorts Stratified by treatment complexity at index. (27 tables, 3 outcomes x 3 strata by treatment complexity at index x 3 countries)	As treated exposure definition	Main outcomes- Table 8	Table 25

Analysis	Details	Exposure definition	Outcomes	Template
Hazard ratio estimates using adjusted model	
Using matched cohorts
 
Stratified by PS quartiles at index.
 
(36 tables, 3 outcomes x 4 strata by propensity score quartiles x 3 countries)
	As treated exposure definition	Main outcomes- Table 8	Table 25
Hazard ratio estimates using adjusted model	
Using matched cohorts
 
Stratified by age category at index.
 
(63 tables, 3 outcomes x 7 strata by age category x 3 countries)
	As treated exposure definition	Main outcomes- Table 8	Table 25
Hazard ratio estimates using adjusted model	
Using matched cohorts
 
Stratified by gender.
 
(18 tables, 3 outcomes x 2 strata by gender x 3 countries)
	As treated exposure definition	Main outcomes- Table 8	Table 25
Hazard ratio estimates using adjusted model	
Using matched cohorts
 
Stratified by insulin use at index.
 
(18 tables, 3 outcomes x 2 strata by insulin use at index x 3 countries)
	As treated exposure definition	Main outcomes- Table 8	Table 25
Meta-analyses for adjusted HR estimates	
Using adjusted HR estimates and 95% CIs from all study countries.
 
For each stratification variable listed above.
 
(54 figures, 3 outcomes x (3+4+7+2+2) strata)
	As treated exposure definition	Main outcomes- Table 8	Figure 8
Secondary objectives:				
Descriptive analysis				

Analysis	Details	Exposure definition	Outcomes	Template
Stratified incidence rates	Using matched cohorts Country specific analysis (9 tables, 3 outcomes x 3 countries)	Cumulative exposure dose of empaglifloz in	Main outcomes- Table 8	Table 30
Stratified incidence rates	Using empagliflozin users subgroup Country specific analysis (9 tables, 3 outcomes x 3 countries)	Empaglifloz in daily dose	Main outcomes- Table 8	Table 31
Stratified incidence rates	Using empagliflozin users subgroup Country specific analysis (9 tables, 3 outcomes x 3 countries)	Cumulative exposure duration to empaglifloz in	Main outcomes- Table 8	Table 32
Meta-analysis of incidence rates	Using pooled number of outcome events and person-time from all study countries (9 tables, 3 outcomes x 3 secondary exposure definitions)	The secondary exposure definitions listed above	Main outcomes- Table 8	Table 30- Table 32
Secondary objectives: Comparative analysis				
Hazard ratio estimates using adjusted model	Using matched cohorts Country specific analysis (9 tables, 3 outcomes x 3 countries)	Cumulative exposure dose of empaglifloz in	Main outcomes- Table 8	Table 26
Hazard ratio estimates using adjusted model	Using matched cohorts Country specific analysis (9 tables, 3 outcomes x 3 countries)	Empaglifloz in daily dose	Main outcomes- Table 8	Table 27

Analysis	Details	Exposure definition	Outcomes	Template
Hazard ratio estimates using adjusted model	Using matched cohorts Country specific analysis (9 tables, 3 outcomes x 3 countries)	Cumulative exposure duration to empagliflozin	Main outcomes- Table 8	Table 28
Meta-analysis of adjusted HR estimates	Using adjusted HR estimates with 95% CIs from all study countries (9 figures, 3 outcomes x 3 secondary exposure)	3 secondary exposure definitions listed above	Main outcomes- Table 8	Figure 8

Sensitivity analysis: NCC study design

Balance assessment for baseline characteristics between matched cases and controls.	Country specific analysis (3 tables, one for each country)	N/A	N/A	Table 33
Odds ratio using conditional logistic regression	Nested case-control study design. (3 tables, 1 outcome (all cancer cases) x 3 countries)	As treated exposure definition	All cancer cases defined in Table 8	Table 34
Meta-analysis for odds ratio estimates	Using odds ratio estimates with 95% CIs from all study countries (1 figure, 1 outcome (all cancer cases))	As treated exposure definition	All cancer cases defined Table 8	Figure 8

Analysis	Details	Exposure definition	Outcomes	Template
Sensitivity analysis: Adjusting for time-dependent confounding				
Hazard ratio estimates using marginal structural model	Using matched cohorts MSM using IPTW. (3 tables, 1 outcome x 3 countries)	As treated exposure definition	Urinary tract cancer as defined in Table 8	Table 35
Meta-analysis of adjusted HR estimates using MSM	Using adjusted HR estimates with 95% CIs from all study countries (1 figure, 1 outcome)	As treated exposure definition	Urinary tract cancer as defined in Table 8	Figure 8
Sensitivity analysis: Exposures				
Hazard ratio estimates using adjusted model	Using matched cohorts (3 tables, 1 outcome x 3 countries)	Intention to treat exposure definition	Urinary tract cancer as defined in Table 8	Table 25
Meta-analysis of adjusted HR estimates	Using adjusted HR estimates with 95% CIs from all study countries (1 figure, 1 outcome)	Intention to treat exposure definition	Urinary tract cancer as defined in Table 8	Figure 8
Sensitivity analysis: Grace period				
Hazard ratio estimates using adjusted model	Using matched cohorts Allowed gaps between exposure episodes extended to 90 days (3 tables, 1 outcome x 3 countries)	Intention to treat exposure definition	Urinary tract cancer as defined in Table 8	Table 25
Meta-analysis of adjusted HR estimates	Using adjusted HR estimates with 95% CIs from all study countries (1 figure, 1 outcome)	Intention to treat exposure definition	Urinary tract cancer as defined in Table 8	Figure 8

Analysis	Details	Exposure definition	Outcomes	Template
Sensitivity analysis:				
Outcomes				
Crude incidence rates	Using matched cohorts Country specific analysis (9 tables, 3 outcomes x 3 countries)	As treated exposure definition	Further outcomes- Table 9	Table 29
Hazard ratio estimates using adjusted model	Using matched cohorts (3 tables, 3 outcomes)	As treated exposure definition	Further outcomes- Table 9	Table 25
TNM staging at diagnosis	Using matched cohorts (9 tables, 3 outcomes x 3 countries)	As treated exposure definition	Further outcomes- Table 10	Table 21
Albuminuria tests each year	Using matched cohorts (3 tables, 3 countries)	As treated exposure definition	NA	Table 36
Sensitivity analysis:				
Extended latency period				
Hazard ratio estimates using adjusted model	Using matched cohorts Duration of latency period is extended to 12 months. (3 tables, 1 outcome x 3 countries)	As treated exposure definition	Urinary tract cancer as defined in Table 8	Table 25
Meta-analysis of adjusted HR estimates	Using adjusted HR estimates with 95% CIs from all study countries (1 figure, 1 outcome)	As treated exposure definition	Urinary tract cancer as defined in Table 8	Figure 8
Hazard ratio estimates using adjusted model	Using matched cohorts Discontinuation is 6 months after last day of medication or switch. (3 tables, 1 outcome x 3 countries)	As treated exposure definition	Urinary tract cancer as defined in Table 8	Table 25
Meta-analysis of adjusted HR estimates (discontinuation is 6 months after last day of medication or switch)	Using adjusted HR estimates with 95% CIs from all study countries (1 figure, 1 outcome)	As treated exposure definition	Urinary tract cancer as defined in Table 8	Figure 8

Analysis	Details	Exposure definition	Outcomes	Template
Sensitivity analysis: Inclusion of the Aurum CPRD database				
Description of patient baseline characteristics for the UK, stratified by CPRD database	CPRD specific analysis (1 table)	N/A	N/A	Table 37
Stratified incidence rates	Using UK matched cohorts (3 tables, 3 outcomes x 1 country)	As treated exposure definition	Main outcomes- Table 8	Table 38
Hazard ratio estimates using crude model after adding CPRD database as a stratification variable	Using UK matched cohorts (3 tables, 3 outcomes x 1 country)	As treated exposure definition	Main outcomes- Table 8	Table 39
Hazard ratio estimates using the base model after adding CPRD database as a stratification variable	Using matched cohorts Only for the UK (3 tables, 3 outcomes x 1 table)	As treated exposure definition	Main outcomes- Table 8	Table 40
Hazard ratio estimates using the adjusted model after adding CPRD database as a stratification variable	Using matched cohorts Only for the UK (3 tables, 3 outcomes x 1 table)	As treated exposure definition	Main outcomes- Table 8	Table 41
Hazard ratio estimates using the crude model, stratified by UK-CPRD databases	Using UK matched cohorts (3 tables, 3 outcomes x 1 country)	As treated exposure definition	Main outcomes- Table 8	Table 42
Hazard ratio estimates using the base model, stratified by UK-CPRD databases	Using UK matched cohorts (3 tables, 3 outcomes x 1 country)	As treated exposure definition	Main outcomes- Table 8	Table 43
Hazard ratio estimates using the base model, stratified by UK-CPRD databases	Using UK matched cohorts (3 tables, 3 outcomes x 1 country)	As treated exposure definition	Main outcomes- Table 8	Table 44
Sensitivity analysis: Meta-analysis using fixed-effect model				

Analysis	Details	Exposure definition	Outcomes	Template
Meta-analysis of adjusted HR estimates using a fixed-effect model	Using adjusted HR estimates and 95% CIs from all study countries (3 figures, 3 outcomes)	As treated exposure definition	Main outcomes- Table 8	Figure 9

